Network-Level Mechanisms for Preclinical Alzheimer's Disease Development

Principal Investigator: [name] (Department of Biophysics)

Co-investigator: [name] (Department of Neurology)

Address

Medical College of Wisconsin
[name]
[name]

Funding Sponsor: National Institutes of Health, National Institute on Aging (R21 AG 056882)

Version: 5

Version Date: April 1, 2019

Replaces Version: 4, September 21, 2018

PROTOCOL SUMMARY

Title	Network-Level Mechanisms for Preclinical Alzheimer's Disease Development
Principal Investigator	[name]
Study Site	Medical College of Wisconsin
Clinical Trial Phase	Phase II
Study Disease	Alzheimer's disease
Main Eligibility Criteria	
 • Fluent in English • At least 8 years of education • Healthy APOE 4 carriers and noncarriers • Age 55–75 years • Normal cognitive function • Free of neurological or psychiatric comorbidities
Study Rationale	
Levetiracetam (LEV) is a generic drug used in long-term epilepsy treatment, with known pharmacokinetic and pharmacodynamic properties. It is relatively safe and has an acceptable side-effect profile. A novel extended release formulation of AGB101 (220 mg of levetiracetam) was developed to allow for once-daily dosing in amnestic mild cognitive impairment (aMCI). So far, no studies have been conducted to see if a low dose of AGB101 can effectively reduce the network dysfunction in cognitively normal subjects who are APOE 4 carriers. The pre-dementia state among APOE 4 carriers can be identified by measuring abnormal brain connectivity with functional MRI. Considering this, use of AGB101 to reduce the network dysfunction in cognitively normal subjects who are APOE 4 carriers should be explored.

Primary Objectives	To determine whether normalization of resting-state connectivity can be achieved in APOE 4 carriers with 2 weeks AGB101 (220 mg, QD) treatment compared with APOE 4 noncarriers receiving the same treatment
Secondary Objectives	To measure cognitive function in APOE 4 carriers and noncarriers at the beginning and end of treatment with placebo

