4.1. Overall Design

This study will test the hypothesis that **decreased abnormal hyperfunctional connectivity can be correlated with improved EM using a daily, low-dose LEV perturbation (AGB101 levetiracetam extended release)**. In this study, there are two study groups: APOE 4 carriers ($n=25$) and APOE4 noncarriers ($n=25$). The functional connectivity changes in HFC will be determined in a randomized, double-blind, placebo-controlled crossover manner, in which a low dose of AGB101 levetiracetam extended release (220 mg, QD) or placebo is administered to 50 healthy 55-75-year-old subjects (comprising 25 APOE 4 carriers and 25 noncarriers), with the order of treatments counterbalanced in a within-subject crossover design, as illustrated in

Fig. 2 below. The study procedures are almost identical to those described in Refs (77, 78). In brief, study participants will receive placebo during one treatment period and AGB101 levetiracetam extended release during the other treatment period, with the order of treatments counterbalanced (randomized, double-blind).

Figure 2. Study design and AGB101 treatment protocol

Notes: Of the 50 subjects, 25 are APOE 4 carriers and 25 are noncarriers.

See Table 1 for timing and schedule of procedures.

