6.3. Functional-Connectivity Changes Due to Perturbation. We employed age, years of education, gender, and gray matter (GM) volume as time-invariant covariates to obtain residual variables to determine the HFC changes due to perturbation. We will model the HFC as a function of these nuisance regressors, using the following multiple linear regression equation, and retain the residuals as $HFC_{Res}^+(s, g, t)$ for further analysis:

$$HFC(s, g, t) = \beta_0 + \beta_1 Age(s) + \beta_2 Edu(s) + \beta_3 GM(s) + \beta_4 CSF(s) + \beta_5 Gender(s) + Res(s, g, t),$$

where $\widetilde{HFC}^+(s, g, t) \equiv Res(s, g, t)$. This regression will be performed using all of the data (i.e., all subjects, all groups, and all times). The GM measurement will be conducted with GM concentration and hippocampal volume measurement, as described in our publication and others (71-74). We will test the residuals $\widetilde{HFC}^+(s, g, t)$ using three-factor crossed-nested analysis of variance (ANOVA), with fixed factors of group and

time and a random factor of *subject* nested within *group* (i.e., all subjects will be tested at all times, but the placebo and AGB101groups will contain different treatment phases). We will test for both group and time main effects, as well as for the group \times time interaction. If we find significant main effects or interactions, we will perform post hoc procedures to determine which time and group (i.e., placebo vs. AGB101) combinations are significantly different. In addition to the HFC analysis, we will conduct a DMN analysis 75).

6.4. EM Changes Due to AGB101Perturbation. The two EM scores (AVLT and LMT) will be normalized to Z-score by transforming individual raw test scores according to the mean and standard deviation of the scores for all subjects. Then, Z-scores of each test will be averaged to obtain individual composite memory Z-score, as we have previously published (76). Similar to the above model for HFC changes due to AGB101perturbation, we will model the Cog score, using the time-invariant covariates as nuisance regressors:

$$\Delta EM(s, g, t) = \beta_0 + \beta_1 Age(s) + \beta_2 Edu(s) + \beta_3 GM(s) + \beta_4 CSF(s) + \beta_5 Gender(s) + Res(s, g, t)$$

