5.4.7. Randomization, Study Drug Dispensation, Administration, and Compliance

The Investigational Drug Service at Froedtert Hospital will randomize participants to the treatment conditions.

In Period 1, all study participants will receive treatment with either AGB101 (220 mg, orally, QD) or placebo; in Period 2, all subjects will crossover and receive the other treatment. This is a double-blind study, so both the participants and study team will be blind to the treatment received.

All study treatments (drug and placebo) are dispensed in identical nondescript tablets by the Investigational Drug Service at Froedtert Hospital. Tablets are provided for daily morning doses. Study drugs will be dispensed at baseline and on the last day of the 4-week (-+ 1 week) washout period. Subjects will be asked to self-administer treatment QD, once in the morning.

Treatment compliance will be monitored by participant self-report at the end of each treatment phase, bottle return and pill count, and analysis of AGB101 blood values at each visit during the study protocol.

Data Management

6.1. The Froedtert Hospital Investigational Pharmacy system will be used to enroll patients and obtain the randomly assigned treatment group. Data forms will be printed, completed, and entered into a database. The database will be monitored for completeness, consistency, accuracy, and timeliness. No patient-identifying information will be stored in the database. To ensure that data are secure from external violation, computer systems containing study data will be password protected, and physical access to the computer systems will be limited.

6.2. Determination of Changes in Network Activity and Concurrent Improvement in EM. The cognitive and MRI/rfMRI datasets will be obtained at baseline (before placebo/AGB101 administration) and on the last day of each 2-week treatment period. These two time points will be denoted $t = 1, 2$. The two 25-subject groups, both of which will receive both placebo and AGB101 at different treatment phase, will be denoted $g = 1, 2$. The set of EM scores for subject s , from group g , at time t will be denoted $Cog(s,g,t)$, where $s = 1, \dots, 25$; $g = 1, 2$; and $t = 1, 2$. The HFC calculated between the hippocampus and the bilateral sensorimotor cortex for subject s , from group g , at time t will be denoted $HFC(s,g,t)$.

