6.3. Functional-Connectivity Changes Due to Perturbation. We employed age, years of education, gender, and gray matter (GM) volume as time-invariant covariates to obtain residual variables to determine the HFC changes due to perturbation. We will model the HFC as a function of these nuisance regressors, using the following multiple linear regression equation, and retain the residuals as $HFC_{Res}^+(s, g, t)$ for further analysis:

$$HFC(s, g, t) = \beta_0 + \beta_1 Age(s) + \beta_2 Edu(s) + \beta_3 GM(s) + \beta_4 CSF(s) + \beta_5 Gender(s) + Res(s, g, t),$$

where $\widetilde{HFC}^+(s, g, t) \equiv Res(s, g, t)$. This regression will be performed using all of the data (i.e., all subjects, all groups, and all times). The GM measurement will be conducted with GM concentration and hippocampal volume measurement, as described in our publication and others (71-74). We will test the residuals $HFC^+(s, g, t)$ using three-factor crossed-nested analysis of variance (ANOVA), with fixed factors of group and

time and a random factor of *subject* nested within *group* (i.e., all subjects will be tested at all times, but the placebo and AGB101groups will contain different treatment phases). We will test for both group and time main effects, as well as for the group \times time interaction. If we find significant main effects or interactions, we will perform post hoc procedures to determine which time and group (i.e., placebo vs. AGB101) combinations are significantly different. In addition to the HFC analysis, we will conduct a DMN analysis 75).

6.4. EM Changes Due to AGB101Perturbation. The two EM scores (AVLT and LMT) will be normalized to Z-score by transforming individual raw test scores according to the mean and standard deviation of the scores for all subjects. Then, Z-scores of each test will be averaged to obtain individual composite memory Z-score, as we have previously published (76). Similar to the above model for HFC changes due to AGB101perturbation, we will model the Cog score, using the time-invariant covariates as nuisance regressors:

$$\Delta EM(s, g, t) = \beta_0 + \beta_1 Age(s) + \beta_2 Edu(s) + \beta_3 GM(s) + \beta_4 CSF(s) + \beta_5 Gender(s) + Res(s, g, t)$$

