Define $\widehat{\Delta EM}(s, g, t) \equiv Res(s, g, t)$. We will test the residuals $\widehat{\Delta EM}(s, g, t)$ using a *three-factor crossed-nested* ANOVA, with fixed factors *group* and *time*, and random factor *subject* nested within *group*. We will test for group and time main effects, as well as the group \times time interaction. If we find significant main effects or interactions, we will perform post hoc procedures to determine which time and group combinations are significantly different.

6.5. Prediction of Changes in Correlation Between HFC and EM Before and After AGB101Perturbation. A multiple linear regression is used to model EM as a linear function of HFC and test the difference in slope and intercept between the AGB101and placebo groups. If the subject is in the AGB101group, $I(s, g) = 1$; if the subject is in the placebo group, $I(s, g) = 0$.

$$EM(s, g) = \beta_{0,0} + \beta_{0,1} I(s, g) + \beta_{1,0} HFC(s) + \beta_{1,1} HFC(s)I(s, g) + Res(s)$$

Here, **HFC(s)** represents baseline HFC for subject s (for simplicity, nuisance regressors are not shown).

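### Sections 6.3 and 6.4 let any of three undesignated tests open post hoc comparisons, with no stated alpha or adjustment and no treatment term for the primary objective

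*SAP*

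**What the plan says.** The primary objective in the Protocol Summary is normalization of connectivity in carriers under AGB101, "compared with APOE 4 noncarriers receiving the same treatment". Protocol section 4.1 states that "there are two study groups: APOE 4 carriers ($n=25$) and APOE4 noncarriers ($n=25").

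SAP section 6.2 indexes the data by subject, group and time. It describes group as "The two 25-subject groups, both of which will receive both placebo and AGB101 at different treatment phase". It lists measurements at baseline and on the last day of each treatment period, then writes "These two time points will be denoted $t = 1, 2".

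Section 6.3, the same in both documents, fits an ANOVA to the HFC residuals with group and time as fixed factors and subject nested within group. The protocol says: "We will test for both group and time main effects, as well as for the group" by time interaction. The follow-up rule in the SAP is: "If we find significant main effects or interactions, we will perform post hoc procedures to determine which time and group" combinations differ, and there group is glossed with the words "i.e., placebo vs. AGB101) combinations are significantly different". Section 6.3 also adds a default mode network (DMN) analysis without giving it a rank.

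SAP section 6.4 applies the same three tests to EM: "If we find significant main effects or interactions, we will perform post hoc procedures to determine which time and group combinations are significantly different".

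The documents state no significance level, do not say which of the three tests is decisive, and give no multiplicity method.

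**The concern.** The three tests answer different questions, yet each has the same power to start the search through the cells.

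- With group as genotype, the group main effect is a comparison of non-randomised groups. It can be significant with no drug effect at all.
- Time, as indexed, does not encode treatment. Order is counterbalanced, so a time effect mixes AGB101 sessions with placebo sessions and picks up practice or session effects.
- The group × time interaction is nearest to the objective, but it compares change over visits between genotypes, not the AGB101-minus-placebo difference between genotypes.

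A trial with no drug effect therefore has several routes to a significant result that could be reported as a connectivity change due to AGB101, while the contrast in the primary objective is not formally tested.

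**Working it through.** The plan states no alpha, effect size, SD or power, so there is no figure of its own to reproduce.

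**Inputs from the documents.** 25 carriers and 25 noncarriers (Protocol 4.1). Three omnibus tests, any one opening the post hoc step (6.3). Two indexed time levels but three measured occasions (6.2). Subject random within group (6.3).

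**Assumptions.** Each test at two-sided 0.05. Post hoc tests are unadjusted within-genotype comparisons between times. No time or drug effect. Within-subject correlation 0.5. Genotype difference of 0, 0.5, 0.8 or 1.5 SD. The documents anchor none of these.

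**Closed form, treating the tests as independent.**

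- At least one of three omnibus tests significant with no effects: 1 − 0.95³ = 14.3%.
- Time or interaction significant: 1 − 0.95² = 9.75%.

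**Simulation of the split-plot ANOVA, 40,000 trials per row.** A false change claim is a significant time test, a significant interaction, or a significant gated within-genotype comparison.

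| Time levels | Genotype difference (SD) | Post hoc step opens | Time or interaction significant | Gated post hoc claim alone | Any false change claim |
|---|---|---|---|---|---|
| 2 | 0 | 14.4% | 9.8% | 6.5% | 10.0% |
| 2 | 0.5 | 56.5% | 9.6% | 8.1% | 11.5% |
| 2 | 0.8 | 90.5% | 9.9% | 9.5% | 13.1% |
| 2 | 1.5 | 100% | 9.6% | 9.7% | 13.1% |
| 3 | 0 | 14.2% | 9.5% | 9.2% | 10.3% |
| 3 | 0.5 | 60.5% | 9.5% | 16.6% | 17.8% |
| 3 | 0.8 | 93.2% | 9.7% | 22.2% | 23.3% |
| 3 | 1.5 | 100% | 9.7% | 23.4% | 24.5% |

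Monte Carlo standard error near 13% is √(0.13 × 0.87 / 40,000) = 0.17 points.

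**Where the excess comes from.** With two levels, the gated post hoc step adds 10.0 − 9.8 = 0.2 points at no genotype difference and 13.1 − 9.6 = 3.5 points at 1.5 SD. With three levels it adds 10.3 − 9.5 = 0.8 to 24.5 − 9.7 = 14.8 points, because each genotype then has three pairwise comparisons instead of one.

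**Sensitivity.** With two levels, correlations of 0.2 and 0.8 moved the 0 and 0.5 SD results by less than 0.5 points. Covariate residualisation was not simulated. Because the covariates are constant over time, it subtracts the same amount from all of a subject's sessions and leaves within-subject differences unchanged; it can affect only the group test.

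**Alternatives.** One prespecified test gives 5%. Keeping the gate but applying Bonferroni to the within-genotype comparisons gives 4.0–4.9% for a false post hoc claim with two levels and 3.2–4.6% with three. Removing only the genotype gate still leaves about 9.75%, from the time and interaction tests.

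**The case against.** Four objections have weight.

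1. **A reader might infer that the plan prescribes unadjusted post hoc tests.** It does not. It is silent, and many post hoc procedures carry an adjustment. The percentages are therefore conditional. What stands is that neither the procedure nor the alpha is fixed in advance.

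2. **A reader might blame the 10–13% on the genotype gate.** With two time levels, most of it comes from counting either of two undesignated omnibus tests as a change claim. The gate is the main source of excess only with three occasions and a sizeable genotype difference.

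3. **Group may mean treatment.** The gloss in 6.3, and the AGB101 and placebo groups in 6.5, point that way. On that reading the genotype gate disappears. But subjects cannot then be nested within group, since each receives both treatments, and genotype leaves the model, so the primary objective is again untested. The conflict needs resolving either way.

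4. **A reader might take the preliminary data as showing that carriers and noncarriers differ in mean HFC, so that the gate will usually be open.** Protocol section 3.3 reports differences in association: different neural correlates of EM by genotype, and a link between baseline HFC and EM decline in carriers only. It reports no mean difference in sensorimotor HFC. The expectation of one rests on the hyperconnectivity premise in Protocol section 1, so the SD values above are assumptions.

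Context also counts. This is a 50-subject mechanistic study with one primary outcome and region named in Protocol section 1.3, which lowers the stakes of strict error control. It does not remove the need for a decisive test.

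**Conclusion.** The point holds as a should-fix. Any of three tests, none designated primary, opens the cell comparisons for both HFC and EM, and no alpha or adjustment is stated. On the section 6.2 reading of group, a genotype difference unrelated to the drug is enough to open them, and no term tests AGB101 against placebo.

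At 0.05 per test with unadjusted follow-up, the chance of a false change claim is about 10–13% with two time levels over an assumed genotype difference of 0 to 1.5 SD, and about 10–25% with three. Counting only gated post hoc claims, the two-level figure is about 6–10%. The documents do not support quoting these as the plan's actual error rate: alpha, adjustment, genotype difference and number of time levels are all unsettled. The structural defect does not depend on them.

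**What to change.** In section 6.3:

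- Define group as genotype throughout and remove the placebo versus AGB101 gloss.
- Code treatment (AGB101 or placebo) by period, and state how many occasions enter the model and what role the baseline scan has.
- Name one primary test: the AGB101-minus-placebo by genotype contrast on HFC, at two-sided 0.05.
- Report genotype and visit main effects descriptively, not as gates.
- Run within-genotype AGB101-versus-placebo comparisons only after the primary test and with a stated adjustment, for example Holm.

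Use the same structure for EM in 6.4, as secondary, and label the DMN analysis exploratory.

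No new data, visits or subjects are needed. This is more than rewording, because the present ANOVA has no treatment term, but the model change is small. The price is fewer routes to a nominally significant result. The contrast between genotypes is also less precise than a within-carrier comparison: with 25 per group and equal variance of the treatment differences, its standard error is √(2σ²/25) against √(σ²/25), a factor of √2. Of the options, it is the one that matches the stated primary objective.

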6.6. Expected Results, Deliverable, and Problems

Through this study, we expect to realize two goals: **Scientifically**, we will demonstrate that aberrant HFC represents a primary upstream mechanism that may contribute to cognitive deficits in CN APOE 4 carriers. Further, we will demonstrate that changes in the dysfunctional hippocampal network upon AGB101perturbation can be quantified as a biomarker for measuring network responses. **Clinically**, we expect that the short-term changes in network activity after the 2-week perturbation period will lead to a decrease in HFC, and possibly to cognitive improvement. This study can provide conceptual proof for preventive intervention. Using the predictive relationship between HFC and the EM changes, individuals carrying the APOE 4 allele can then be stratified into high and low HFC activity subgroups to further refine the subpopulation. Also, this study will provide information and address the power of adequate enrollment, protocol adherence, subject retention, and safety for future pilot trials.

We may be able to detect HFC changes in the 2-week period after AGB101perturbation as a primary outcome, but we may not be able to detect significant EM changes as the secondary outcome in this short R21 funding mechanism. In a future study, we could extend follow-up to 26 weeks or a year to enable us to detect the slowly declining EM functions.

7. DATA SAFETY MONITORING PLAN

An appointed DSMB will discuss the ethical conduct of the trial, review event definitions and the subject ICF form, and further develop plans for monitoring the data and safety of the trial. The DSMB will meet at least every six months to review the course of the trial and interim data. The DSMB agrees to communicate with institutional review board (IRB)/human subject committees to provide reassurances, as appropriate. There will be three DSMB members with the following areas of expertise:

- Neural mechanism underlining learning and memory in aging and neurological disease
- Aging and memory loss
- Psychology and neuroimaging
